4.4.13 Secondary Endpoint 13: Aneurysm Occlusion

Endpoints: Angiographic assessment of aneurysm occlusion grade according to the Raymond-Roy classification scale, parent-vessel compromise, and occlusion durability as assessed from an independent core laboratory. This endpoint is assessed post-procedure and at 180-day follow-up.

Subjects to Include: Analysis Cohort

Statistical Analysis: The frequency and proportion of each summary (aneurysm grade, parent-vessel compromise, occlusion durability) along with a 2-sided Clopper Pearson Exact 95% confidence interval will be summarized. Note the confidence interval for summaries of categories with more than 2 categories will be binomial confidence interval for each individual category compared to the rest.

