##### Post-CorPath Procedure Subject Evaluations

- NIH Stroke Scale (NIHSS) and Modified Rankin Scale (mRS) conducted by a trained person with appropriate qualifications to perform these evaluations are required to be performed within 24-hours post procedure or prior to discharge, whichever occurs first.
- Raymond Grade-Roy Occlusion Classification Scale conducted by a trained person with appropriate qualifications to perform this evaluation:
  - Class (I): Complete occlusion – complete obliteration of the aneurysm
  - Class (II): Residual neck – persistence of any portion of the original defect of the arterial wall as seen on any single projection, but without opacification of the aneurysmal sac.
  - Class (III): Residual aneurysm – opacification of the aneurysmal sac.
    - Class IIIa: contrast opacification within the coil mesh
    - Class IIIb: contrast opacification outside coil mesh
- Additional post procedure clinical assessment (scales/scores) is left to the discretion of the investigator and shall be dictated by the patient's clinical symptoms
- Record of all Adverse Events (AEs)
- If clinically indicated by the Investigator and/or if performed under standard hospital procedure, record lab values closest to 24-hours post-procedure or discharge:
  - Hemoglobin (HGB)
  - Hematocrit (HCT)
  - Activated Partial Thromboplastin Time (aPTT)
  - Platelet count
  - International Normalized Ratio (INR)
  - Serum Creatinine
  - Glomerular Filtration Rate (GFR)

- Before the subject is discharged from the hospital, it is recommended that telephone numbers and contact information be confirmed with the subject (and/or authorized legal guardian) to ensure the ability to contact him/her after discharge from the hospital for scheduling of the 90-day ( $\pm$  14 days) telephone evaluation.

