#### 4.8.10 Follow-Up Evaluations

The following assessments will be completed at the specified time points below.

- 90-Day Follow-Up ( $\pm$  14 days) via a telephone evaluation**
  - Functional outcomes assessment to include Modified Rankin Scale (mRS)
  - Record any adverse events or additional interventions since time of hospital discharge
- 180-Day Follow-Up ( $\pm$  30 days)**
  - Digital Subtraction Angiography (DSA), Computed Tomography Angiography (CTA), or Magnetic Resonance Angiography (MRA) / Magnetic Resonance Imaging (MRI) of the brain/head
  - Functional outcomes assessment to include Modified Rankin Scale (mRS)
  - Raymond-Roy Occlusion Classification
  - Record any adverse events or additional interventions since time of hospital discharge.

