**Table 5. Safety and Effectiveness data 180-day rates presented.**

Pipeline for Uncoilable or Failed Aneurysms Clinical Trial Becske et al 2013. 	N	180-day Results (%)
SAFETY		
• Ischemic stroke (perioperative) related to PED-associated thrombosis (patient later experienced delayed fatal hemorrhage after traumatic fall in rehabilitation facility)	107	2.8% (3/107)
• Ischemic stroke (delayed) secondary to major in-construct (PED) stenosis		---
• Ischemic stroke (delayed) from noncompliance with the required oral antiplatelet regimen		---
• Ipsilateral intraparenchymal hemorrhage (perioperative)		1.9% (2/107)
• Ipsilateral intraparenchymal hemorrhage (delayed) on day 14 (fatal)		---
• Rapidly fatal event possibly neurologic in origin		0.9% (1/107)
EFFECTIVENESS	N	180-day Aneurysm
• Angiographic evaluation that demonstrated complete aneurysm occlusion and absence of major stenosis at 180 days	106	
○ YES		73.6% (78/106)
○ NO		26.4% 28/106

The goal of the Pipeline trial safety analysis was to show the rate of ipsilateral stroke or neurologic death is statistically lower than 20%. The rate of complete aneurysm occlusion analysis goal was set at a threshold of 50%. The Pipeline trial demonstrates that treatment of large and giant cerebral aneurysms is feasible and effective, with a reasonable margin of safety. Patient follow-up for the trial consisted of repeat neurologic examinations at 30 and 180 days after device placement and a follow-up telephone call evaluation at 90 days. Further periodic follow-up visits were scheduled (through 5 years). Patients underwent conventional angiography and a neurologic examination at 180 days. In this study, the 180-day follow-up data imply that fewer angiographic follow-up visits are required.

Version Date: May 21, 2021

*This confidential document is the property of Corindus, Inc. and shall not be reproduced, distributed, disclosed or used without the express written consent of Corindus, Inc.*

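### SAP 4.4.13 tabulates an aneurysm successfully retreated before the 180-day image as occluded, leaves occlusion durability undefined, and pools 180-day imaging methods

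*SAP*

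**What the plan says.** SAP 4.4.13 defines Endpoint 13 as "Angiographic assessment of aneurysm occlusion grade according to the Raymond-Roy classification scale, parent-vessel compromise, and occlusion durability as assessed from an independent core laboratory". On timing it states: "This endpoint is assessed post-procedure and at 180-day follow-up". For the output it says "The frequency and proportion of each summary (aneurysm grade, parent-vessel compromise, occlusion durability) along with a 2-sided Clopper Pearson Exact 95% confidence interval will be" tabulated, with each category of a multi-category item set against the rest. The subjects are the Analysis Cohort, which SAP 4.1 defines by a recorded robotic microcatheter insertion time. Nothing that happens later changes a subject's membership or grade.

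Protocol 4.8.10 gives the same instruction at the 90-day and 180-day contacts: "Record any adverse events or additional interventions since time of hospital discharge". Protocol 5.6 lists recanalization and residual flow among the anticipated events.

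On imaging, Protocol 4.8.10 allows DSA, CTA, or "Magnetic Resonance Angiography (MRA) / Magnetic Resonance Imaging (MRI) of the brain/head" at 180 days. At the index procedure, the Schedule of Activities lists catheter angiography, and its footnote 5 specifies anterior-posterior, lateral and working views for the core laboratory. The procedure workflow in Protocol 4.8.5 includes a final control angiogram.

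SAP section 5 promises effort to obtain complete 90-day and 180-day data. It gives no rule for retreatment or for imaging method.

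**The concern.** Endpoint 13 is the trial's only anatomical measure of whether the treatment lasted. Two things can make the 180-day table say something other than how the index robotic procedure held up.

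First, an aneurysm may recanalize and be treated again before the 180-day image. If the second treatment works, the core laboratory reads an occluded aneurysm, and the table credits that result to the index procedure. The protocol collects the information needed to separate such cases, but the analysis does not use it.

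Second, durability is naturally understood as a comparison of the 180-day grade with the post-procedure grade. One side of that comparison is always catheter angiography. The other may not be, so a shift in class can come from the method as well as from the aneurysm.

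If these rules are chosen only after the 180-day images have been read, the choice is open to the criticism that it followed the result.

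**Working it through.** **The plan's own figures.** Neither document states a sample size, threshold or expected rate for Endpoint 13. The only figure borrowed here is the trial size of 108, which reproduces. With p0 = 0.80, p1 = 0.90 and one-sided alpha 0.025, N = [(1.960 × √(0.80 × 0.20) + 0.842 × √(0.90 × 0.10)) / 0.10]² = 107.4, so 108. It serves below only as a denominator.

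**Following the text for one subject.**
1. A robotic microcatheter insertion time is recorded, so the subject is in the Analysis Cohort (SAP 4.1).
2. The target aneurysm is retreated between discharge and the 180-day image. The intervention is recorded (Protocol 4.8.10).
3. The 180-day scan goes to the core laboratory (Schedule of Activities, footnote 7) and is read as Class I.
4. SAP 4.4.13 counts the grade. No step removes, recodes or flags it.
5. Durability is also tabulated, but neither document defines it. The core-laboratory task list in Protocol 11.4 does not mention durability or retreatment.

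The 180-day grade entry is therefore determined: occluded. The durability entry is not determined.

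**Size of the retreatment effect.** Each such aneurysm contributes 1/n. At n = 108 with all subjects imaged, 1/108 = 0.93 points. The documents give no retreatment rate, so the counts below are assumptions. The starting level of 79/108 is arbitrary; it was chosen to lie near the one 180-day occlusion figure printed in the protocol (78/106 = 73.6%). Intervals are Clopper-Pearson.

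| Retreated and read as Class I (assumed) | Complete occlusion after recoding | 95% CI |
|---|---|---|
| 0 | 79/108 = 73.1% | 63.8 to 81.2 |
| 1 | 78/108 = 72.2% | 62.8 to 80.4 |
| 3 | 76/108 = 70.4% | 60.8 to 78.8 |
| 5 | 74/108 = 68.5% | 58.9 to 77.1 |

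One to five retreated aneurysms (about 1% to 5% of 108) thus move the rate by 0.9 to 4.6 points (5/108 = 4.6). The effect has one sign: recoding can lower the as-observed rate or leave it unchanged, never raise it.

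**Size of the modality effect.** Let p be the complete-occlusion rate by catheter angiography and s the share imaged otherwise. Let sens be the chance that another method shows a residual that is present, and spec the chance that it reads a complete occlusion as complete. Then:

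apparent rate = (1 − s) × p + s × [p × spec + (1 − p) × (1 − sens)]

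The documents give none of s, sens or spec. The assumed ranges are s from 0.25 to 1.00, sens from 0.70 to 0.95 and spec from 0.90 to 1.00, with p = 0.736. The extremes are:
- s = 1, sens = 0.70, spec = 1.00: 0.736 + 0.264 × 0.30 = 0.815, a shift of +7.9 points.
- s = 1, sens = 0.95, spec = 0.90: 0.736 × 0.90 + 0.264 × 0.05 = 0.676, a shift of −6.0 points.

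The sign depends entirely on the assumed accuracies. If every subject has DSA at 180 days, s = 0 and there is no shift.

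**The case against.** The strongest reply is that Endpoint 13 is one of 13 descriptive secondary endpoints, with no hypothesis or threshold. A Class I reading at 180 days is also a true description of that day. Retreatment would not vanish from the report either, because a recanalization recorded as an adverse event appears in the Endpoint 10 tables. A shift of 1 to 5 points lies inside the interval of 63.8 to 81.2 in the illustration. All of this is fair, and it limits the importance of the point. It does not remove it: the adverse event tables are not linked to Endpoint 13, and a one-directional bias is not excused by being smaller than the sampling error.

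Several stronger readings are tempting, and the documents do not support them.

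- A reader might infer that the plan counts retreated aneurysms as durably occluded. It does not say so. Durability is listed separately from grade, assigned to the core laboratory and left undefined, so its handling is unknown.
- A reader might infer that an MRI without angiographic sequences cannot be graded, since Class II describes persistence "as seen on any single projection, but without opacification of the aneurysmal sac". What such a scan can show is not in the documents. SAP 4.4.13 already requires an angiographic assessment, and Protocol 4.8.10 names MRA and MRI together. Gradability belongs to the core laboratory.
- A reader might treat the 73.6% in Protocol Table 5 as a benchmark, because of that trial the protocol says: "Patients underwent conventional angiography and a neurologic examination at 180 days". But Protocol 6.7 uses Table 5 only as a tabular format, where appropriate. The figure also combines complete occlusion with absence of major stenosis, for a different device in uncoilable or failed aneurysms. Matching the modality would not make it comparable.
- A reader might cite Protocol 4.1, which leaves additional treatment to the physician, as proof that early retreatment is expected. The sentence can equally be read as describing care outside the protocol. The interventions recorded under 4.8.10 are firmer ground.

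**Conclusion.** The concern holds in a limited form. Followed as written, SAP 4.4.13 enters an aneurysm successfully retreated before the 180-day image as occluded, and no definition of durability corrects this. Each case adds about 0.9 points at 108 imaged subjects. An assumed 1 to 5 cases add 0.9 to 4.6 points, provided every retreated aneurysm is read as Class I. Those counts are assumptions, since the documents give none.

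The modality mismatch is real but affects only subjects not imaged by DSA at 180 days. Their number is unknown and the direction of the effect is not fixed; the range of −6.0 to +7.9 points rests wholly on assumed accuracies.

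The point concerns the interpretation of one descriptive endpoint. It has no bearing on the two primary endpoints, their performance goals or the sample size. It is worth making because a better analysis is available almost entirely from data already planned for collection.

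**What to change.** Amend SAP 4.4.13 before the 180-day readings are summarized:

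1. Define occlusion durability as the change in core-laboratory Raymond-Roy grade from post-procedure to 180 days. Count any target aneurysm retreated before the 180-day image as not durably occluded, in both the durability summary and the 180-day complete-occlusion summary. Report the number retreated, and keep the as-observed 180-day grade alongside.
2. Record the modality of the 180-day image. Tabulate grade and durability by modality, with a DSA-only sensitivity summary. Leave the decision on whether a scan can be graded to the core laboratory.

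It is also worth checking that the follow-up forms, which are not among the documents, show whether a recorded intervention was on the target aneurysm and when it took place.

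The cost is a few sentences of SAP text and one extra data field, with no added imaging. The downside is a slightly lower reported occlusion rate if any aneurysm is retreated, and smaller groups in the tables by modality.

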4.5 Additional Summaries

Some additional summaries will be prepared:

- Descriptive statistics of the population
 - Demographics and patient baseline characteristics

- Aneurysm characteristics
- Procedures performed
- Malfunctions
- Protocol deviations

5 Data Conventions and Missing Data

It is assumed that because the primary and most secondary analyses are evaluated within twenty-four (24) hours of CorPath GRX procedure or prior to hospital discharge, whichever occurs first, there will be no missing data. For the 90-day and 180-day secondary endpoints (modified Rankin Scale, thromboembolic events, and aneurysm occlusion), all practical monitoring and follow-up steps will be taken to ensure complete and accurate data collection. Additionally, all data collected on safety or adverse events will be reported to the extent they are available.

6 Appendix 1: Adverse Event Classification and Definitions

An Adverse Event (AE) is any untoward medical occurrence, unintended disease or injury, or untoward clinical signs (including abnormal laboratory findings) in subjects, users or other persons, whether or not related to the investigational medical device.

A Serious Adverse Event (SAE), as per the European Standard ISO 14155 (E), is an AE that:

- Led to death
- Led to a serious deterioration in the health of a patient that:
- Resulted in a life-threatening illness or injury
- Resulted in a permanent impairment of a body function or body structure
- Required in-patient hospitalization or prolonged hospitalization
- Resulted in medical or surgical intervention to prevent permanent impairment to a body function or body structure
- Led to fetal distress, fetal death or a congenital abnormality or birth defect.

In the current study indication, a SAE can be defined as an adverse event where the outcome is one of the following:

- Incidence of death 24 hours post procedure
- Target aneurysm rupture
- Vessel perforation
- Vessel dissection
- Thromboembolic complication
- Failure to navigate to target
- Device failure to respond to input, or other intra-operative device failure

Adverse Event Assessments

Relatedness:

- Procedure-related: Event has a strong temporal relationship to the study procedure. This includes AEs attributable to any device(s) used at procedure, such as access devices, delivery microcatheters, embolic coils, non-ionic contrast, guidewires, or any other adjunctive, approved/cleared device for treatment of intracranial aneurysms.
- Device-related: Event has a strong temporal relationship to the CorPath GRX System.
- Unknown: Event relationship cannot be attributed to any of the above categories and remains undetermined.

Procedure -Related Adverse Event

An adverse event is procedure-related when, in the judgment of the Investigator; it is reasonable to believe that the event is not associated with the CorPath GRX System use and is not specific to the device used. Instead, other products, surgical techniques, or medications required

Device-Related Adverse Event

An adverse event is device-related when, in the judgment of the Investigator, the clinical event has a reasonable time sequence associated with use of the CorPath GRX System and is unlikely to be attributed to concurrent disease or other procedures or medications. It is reasonable to believe that the CorPath GRX System directly caused or contributed to the adverse event.

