#### **4.8.8 Device Malfunction Data Collection**

All CorPath GRX System device malfunctions will be documented in the EDC. If the device malfunction is related to a Device-Related Adverse Event (AE), the AE will be entered into the EDC and each site will follow their internal policies for AE reporting.

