### 5.1 Adverse Event Classification and Definitions

An Adverse Event (AE) is any untoward medical occurrence, unintended disease or injury, or untoward clinical signs (including abnormal laboratory findings) in subjects, users or other persons, whether or not related to the medical device (ISO 14155:2011).

NOTE 1: This definition includes events related to the medical device or the comparator.

NOTE 2: This definition includes events related to the procedures involved.

NOTE 3: For users or other persons, this definition is restricted to events related to medical devices.

Disease signs and symptoms that existed prior to study participation are not considered AEs unless the condition recurs after the subject has recovered from pre-existing condition, or the condition worsens in intensity or frequency during the study.

A Serious Adverse Event (SAE), as per the European Standard ISO 14155:2020(E), is an AE that led to any of the following:

- a) Death
- b). Serious deterioration in the health of subject, users or other persons as defined by one or more of the following:
  - 1) a life-threatening illness or injury, or
  - 2) a permanent impairment of a body structure or body function including chronic diseases, or

- 3) in-patient or prolonged hospitalization, or
- 4) medical or surgical intervention to prevent life-threatening illness or injury, or permanent impairment to a body structure or body function,
- c) Foetal distress, foetal death, a congenital abnormality or birth defect including physical or mental impairment.

Planned hospitalization for a pre-existing condition, or a procedure required by the protocol, without serious deterioration in health, is not considered a serious adverse event.

In the current study indication, examples of a Serious Adverse Event (SAE) are:

- Incidence of death 24-hours post procedure
- Target aneurysm rupture
- Vessel perforation
- Vessel dissection
- Thromboembolic complication
- Failure to navigate to target
- Device failure to respond to input, or other intra-operative device failure

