4.2 Primary Effectiveness Endpoint

Objective: To assess effectiveness of using CorPath GRX for robotic-assisted endovascular procedure.

Hypothesis:

$H_0: p \leq 80\% \text{ (90\% - 10\% NI margin)}$

$H_a: p > 80\%,$

where p =proportion of patients with a successfully completed endovascular procedure.

Endpoint: The proportion of subjects with successful completion of the robotic-assisted endovascular procedure absent any unplanned conversion to manual for guidewire or microcatheter navigation, embolization coil(s) or intracranial stent(s) deployment, or an inability to navigate vessel anatomy.

Subjects to Include: Analysis Cohort

Statistical Analysis: The proportion of subjects with a successful procedure completion as defined will be summarized along with a 2-sided Clopper Pearson Exact 95% confidence interval. If the lower bound is greater than 80%, we will declare success and conclude that effectiveness is not inferior to the performance goal of 80%.

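### Navigation and device failures are listed as serious adverse events with no harm condition, so the descriptive SAE breakdown may be inflated and coded inconsistently

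*SAP*

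**What the plan says.** SAP Appendix 1 builds its definitions in layers. The base is the adverse event: "An Adverse Event (AE) is any untoward medical occurrence, unintended disease or injury, or untoward clinical signs". A serious event must then have caused death or fetal harm, or satisfy the limb that begins "Led to a serious deterioration in the health of a patient that", which is followed by a list of qualifying outcomes. Directly below comes a study-specific sentence: "In the current study indication, a SAE can be defined as an adverse event where the outcome is one of the following". Its seven items include "Failure to navigate to target" and "Device failure to respond to input, or other intra-operative device failure".

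Protocol 5.1 has the same structure and the same seven items, introduced by "In the current study indication, examples of a Serious Adverse Event (SAE) are". The glossary in Protocol 13 gives its own SAE definition, based on clinical outcomes, and contains neither technical item.

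Technical failures are also captured elsewhere. Protocol 4.8.8 says "All CorPath GRX System device malfunctions will be documented in the EDC" and has an AE entered when the malfunction is related to a device-related AE. Protocol 4.8.7 records conversions to manual technique with the reason. In SAP 4.2 the events that defeat effectiveness success include unplanned conversion for "embolization coil(s) or intracranial stent(s) deployment, or an inability to navigate vessel anatomy".

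Protocol 5.5 makes sections 5.1 to 5.4 the basis for categorising AEs and sets a 24-hour limit for reporting SAEs to the sponsor. SAP 4.4.10 tabulates AEs by term, split by seriousness and relatedness.

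**The concern.** Two of the seven items describe what the robot failed to do, not what happened to the patient. Taken at face value, a navigation failure that is completed by hand without injury satisfies the list but not the general definition a few lines above it. A coder has textual support for either answer, and with up to 20 sites identical events could be coded both ways.

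The output at stake is the seriousness breakdown in SAP 4.4.10. If technical failures enter it, the table mixes an effectiveness outcome with clinical harm: inability to navigate is already a primary effectiveness failure and would be reported a second time as a serious event. The same wording decides which events fall under the 24-hour reporting rule.

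**Working it through.** **1. The plan's own figures.** The documents state no expected SAE rate, so there is none to reproduce. The sample sizes can be reproduced (SAP 3.2: 80% against 90% for effectiveness, 15% against 5% for safety, two-sided 95% interval), using n = [(z₀.₉₇₅√(p₀q₀) + z_power√(p₁q₁)) / |p₁ − p₀|]².

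- Effectiveness, 80% power: [(1.960 × 0.400 + 0.842 × 0.300) / 0.10]² = 107.4, so 108.
- Safety, 90% power: [(1.960 × 0.357 + 1.282 × 0.218) / 0.10]² = 95.9, so 96.

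Both agree with the plan.

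**2. The definitions side by side**, for a navigation or device failure with no clinical consequence.

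| Place | Is it an SAE? |
|---|---|
| General definition, Protocol 5.1 and SAP Appendix 1 | No: no death, serious deterioration or fetal harm |
| Glossary, Protocol 13 | No: no qualifying outcome |
| Study list, Protocol 5.1 | Yes: named as an example without condition |
| Study list, SAP Appendix 1 | Unclear: named without condition, but the lead-in presupposes an adverse event |
| Protocol 4.8.8 (malfunctions only) | Not by itself: a malfunction record; an AE is entered if one is related to it |

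Protocol 4.8.8 covers malfunctions. A working robot that cannot reach the target is not clearly a malfunction, so navigation failure has no equivalent filter.

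**3. Size.** Inputs: 108 subjects (SAP 3.2) and the coronary conversion rates in Table 4 of both documents. Let q be the share of conversions that match a listed item, involve no harm and are nonetheless coded as serious. Excess SAE subjects = q × rate × 108. The documents do not give q, so the whole range is shown.

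| Conversion rate | Conversions in 108 | Excess, q = 0 | q = 0.5 | q = 1 |
|---|---|---|---|---|
| 1.2% | 0.012 × 108 = 1.3 | 0 | 0.6 | 1.3 |
| 8.3% | 0.083 × 108 = 9.0 | 0 | 4.5 | 9.0 |
| 10.4% | 0.104 × 108 = 11.2 | 0 | 5.6 | 11.2 |

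The excess runs from 0 to about 11 subjects, or 0 to about 10 percentage points.

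**4. Effect on the decision rules.** The primary safety composite in SAP 4.3 consists of rupture, perforation or dissection, and thromboembolic events with neurological decline. Neither technical item is in it. With exact limits at 108 subjects, effectiveness succeeds at 95 or more successes (power 81.0% at a true 90%), and safety succeeds at 8 or fewer events (power 90.8% at a true 5%). SAE coding enters neither count.

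**The case against.** The strongest reply is that the structure already keeps harmless failures out. The SAP list applies to adverse events, and an adverse event must first be a medical occurrence, injury or clinical sign. Malfunctions have their own record and their own summary (SAP 4.5). The Surveillance Committee (Protocol 5.8) adjudicates serious against non-serious as necessary. Because SAP 4.4.10 reports by term, a technical failure under its own term could be told apart from a rupture or a stroke.

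Much of this stands. A reader might infer that every such failure will be counted as an SAE. The documents do not support that; they support only that it may be. A reader might also set about 11 harmless SAEs against the 5.4 subjects implied by the 5% safety rate (0.05 × 108). That comparison fails on both sides. The 11 takes the highest of three coronary rates and assumes that every conversion matches the list and is coded as serious. The 5% belongs to the 24-hour composite, whereas AEs are collected to the end of the study. Nor does the plan compare SAE rates with the manual literature: its tables give mortality, complication, rupture and embolism rates, and there is no SAE performance goal.

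What the reply does not remove is the contradiction. Protocol 5.1 lists both items with no condition, Protocol 5.5 makes that section govern coding, and nothing tells the committee to set the list aside.

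**Conclusion.** The point holds as a conflict of definitions with a bounded, descriptive consequence. Both documents list two technical failures as serious without requiring harm, against their own general definition, the glossary and the malfunction pathway. Such failures may be coded as SAEs, inconsistently across sites.

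The possible excess is 0 to about 11 of 108 subjects. This rests on three assumptions: that coronary conversion rates carry over to intracranial work (the plan says it has no intracranial data), that only conversions matching a listed item count, and that no allowance is made for device failures resolved without conversion, for which the documents give no rate. They do not fix where in the range the trial would fall. The 15% and 80% rules, the 108 subjects and the power are unaffected. It should be corrected, but it does not threaten the primary conclusions.

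**What to change.** Reconcile Protocol 4.8.8, 5.1 and 13 with SAP Appendix 1, in both documents together:

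- A navigation or device failure counts as an SAE in SAP 4.4.10 only when it leads to an outcome that meets the harm-based definition.
- Otherwise it is recorded as a conversion (Protocol 4.8.7) or a malfunction (Protocol 4.8.8) and summarised separately under SAP 4.5. That section already lists malfunctions; a line for conversions needs adding.
- Protocol 5.5 states whether the 24-hour sponsor notification continues to apply to these failures. Protocol 4.8.8 sets no deadline, so simply deleting the items could remove that notification without anyone having decided to do so.

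The cost is wording in two documents and reclassification of any such events already entered. No data are lost, provided that the conversion and malfunction records are kept as planned.
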